8.10 Subgroup Analyses and Effects of Baseline Factors

The subgroup analyses detailed below will be performed within each GT.

To assess the consistency of the response across various subgroups, the SVR₁₂ and SVR₂₄ rates and associated 95% CIs will be estimated within each category of the following baseline factors as classification variables:

- Presence or absence of baseline RAVs to any of the 2 classes of drugs
- Gender (female, male)
- Age (≥ 65 , < 65)
- Race (White, Black or African American, Asian, Other)
- Ethnicity (Hispanic or Latino, not Hispanic or Latino)
- IL28B GT (CC versus non-CC GT)
- HCV RNA at baseline, $\leq 800,000$ IU/mL versus $> 800,000$ IU/mL; ≤ 2 million IU/mL versus > 2 million IU/mL; ≤ 10 million IU/mL versus > 10 million IU/mL
- Stage of fibrosis (non-cirrhotic [F0-F3], cirrhotic [F4])
- HIV co-infection status (HCV/HIV co-infected, HCV mono-infected)
- Treatment-experienced and treatment-naïve
- For GT1 subjects: (GT1a vs. GT1b)
- Geographical Region (US, Canada, European Union, Latin America, Asia Pacific, Middle East – note that regions may be collapsed depending on actual enrollment in the trial)

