2.0 TRIAL DESIGN

2.1 Trial Design

This is a nonrandomized, multi-site, open-label trial to evaluate a novel 2-drug combination regimen (MK-3682 450 mg and MK-8408 [hereafter referred to as ruzasvir (RZR)] 180 mg) in subjects with chronic hepatitis C virus (HCV) to be conducted in conformance with Good Clinical Practices (GCP). Subjects with genotype (GT) GT1, GT2, GT3, GT4, GT5, or GT6 infection will be enrolled. Subjects may be treatment-naïve (TN) or treatment-experienced (TE) with a prior interferon (IFN)-based therapy, but subjects may not have previously received treatment with HCV direct-acting antiviral (DAA) therapy. Subjects may be cirrhotic or non-cirrhotic, and mono-infected with HCV or co-infected with human immunodeficiency virus (HIV). Enrollment will be monitored in real-time, with a target allocation of approximately 25% to 30% cirrhotic subjects for each GT for GT 1-4. As the prevalence of GT5 and GT6 is lower, enrollment of these subjects may be limited. Enrollment of subjects with GT5 and GT6 is approximate with the assumption that full enrollment of these GTs may not be reached, and the proportion of cirrhotic subjects allocated for each of these GT5 and GT6 is not stipulated.

A total of approximately 250 subjects will be allocated to receive 12 weeks of treatment with MK-3682 (450 mg) + RZR (180 mg) (termed MK-3682 + RZR) with target allocation based on GT (GT1, GT2, GT3, GT4, GT5, or GT6) see [Table 1](#).

- The first 50 subjects will be allocated to treatment regardless of GT or fibrosis stage.
- After the first 50 subjects (of any GT) are allocated to treatment, additional allocation will pause to assess general safety and tolerability. This will be assessed after these first 50 subjects complete TW4, as this allows for steady state of drug to be achieved for ≥ 2 weeks. As detailed in Section 5.11.1, this pause in treatment allocation will allow for assessment of any drug-related safety events.
- These first 50 subjects will be included in the overall treatment allocation target of the trial, and counted towards the GT and fibrosis stage allocation targets shown in [Table 1](#).
- If general safety and tolerability is assessed to be acceptable, the remaining 200 subjects will be allocated to treatment with an overall target allocation based on GT (GT1, GT2, GT3, GT4, GT5, or GT6), see [Table 1](#).

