4.2 Rationale

4.2.1 Rationale for the Trial and Selected Subject Population

Currently approved HCV IFN-free DAA regimens, such as LDV/SOF, SOF/VEL, ombitasvir/paritaprevir/dasabuvir/ritonavir+RBV, and EBR/GZR, have better efficacy, tolerability, and convenience than earlier therapies. However, they are not uniformly effective across the 6 HCV GTs. The most effective regimens are for GT1 HCV, which accounts for approximately 46% of infections worldwide [1]. Genotypes 2 and 3 HCV, the next most common GTs, were historically grouped together in treatment guidelines. However, recent studies have shown that infection with GT3, especially in subjects with cirrhosis, is more difficult to treat [25] [8] [9]. In addition, although GT5 and GT6 have a more limited geographic distribution than GT1-4, they predominate in certain regions of the world and represent an unmet medical need with limited clinical experience. In addition, even though several IFN-free combinations are now available for treatment of HCV, clinicians must still take into account the GT and even the subtype, as well as patterns of antiviral resistance in the choice of a regimen. The development of a single, uniform, and pangenotypic regimen that will be safe and effective in all patient populations would represent a substantial advance in the treatment of HCV infection by greatly simplifying treatment paradigms and reducing the need for pretreatment testing and on-treatment monitoring. The clinical potential of the combination of MK-3682 and RZR, both once-daily medications, is suggested by their non-overlapping viral targets, the pangenotypic *in vitro* potencies of both MK-3682 and RZR, the proven success of other HCV NIs in combination with other NS5A inhibitors, and the high efficacy rates from the investigational 3-drug regimen containing MK-3682, GZR, and RZR.

As previously described in Section 4.1.2, the investigational 3-drug regimen containing MK-3682, RZR, and GZR is being explored as a strategy to use 3 DAA agents, each directed at a different target of the hepatitis virus life cycle. As part of a comprehensive clinical development program, the combination of MK-3682 and RZR is currently being evaluated in MK-3682 PN035, an ongoing Phase 2 study characterizing the efficacy and safety profile of MK-3682 at a dose of 450 mg and RZR at a dose of 60 mg for 12 weeks duration. Dosing in PN035 is ongoing, and efficacy results are not yet available. PN041 is designed to explore

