- **HIV Co-infected Subjects:** HIV co-infected subjects are included in this trial because HCV infection is a leading cause of morbidity and mortality among those with HIV-1 [35]. Compared to the general population, the overall prevalence of HCV infection is higher among those infected with HIV-1. In fact, one-fourth to one-third of subjects infected with HIV in the US and Europe are co-infected with HCV [36]. Compared to subjects infected with HCV alone, HIV/HCV co-infected subjects have higher baseline HCV viral loads (VLs) and more rapid progression of liver disease, including more rapid hepatic fibrosis as well as an increased risk of cirrhosis, end-stage liver disease, and hepatocellular carcinoma. Subjects with HIV/HCV co-infection are also more susceptible to developing anemia, and they may have more rapid progression to acquired immunodeficiency syndrome (AIDS) and AIDS-related death [29]. Recent DAA therapies have demonstrated rates of SVR₁₂ that are comparable with those achieved in HCV disease-matched mono-infected subjects. In particular, HIV subjects co-infected with HCV GT1 or GT4 had similarly high efficacy following EBR/GZR therapy in Phase 3 studies compared to those who were not HIV-infected [6]. Given the comparable SVR₁₂ rates observed following all-oral IFN-free DAA regimens in mono-infected and co-infected subjects, HIV/HCV co-infected subjects will be permitted to enroll in this study. A comprehensive set of drug-interaction trials has defined the antiretroviral therapies that can be co-administered with MK-3682, GZR, and RZR (Section 5.5).

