1. Treatment-Related Discontinuation=Failure (TRD=F) approach: Subjects with treatment-related missing data (type #2 above) will be considered as failure; whereas the subjects who have the non-treatment-related missing value (type #3 above) and who do not have virologic failure during the observed study period will be excluded from the analysis for the time points following their study withdrawal. Note that subjects with documented virologic failure during the treatment or follow-up period, even if they withdrew prematurely due to reasons not related to study drug, are classified as failures.
2. Missing=Failure (M=F) approach: Subjects with any non-intermittent missing data (i.e., type #2 and #3 above) will be imputed as failures, regardless of the reason for study discontinuation.

In addition, a missing baseline/Day 1 HCV RNA result will be replaced with a screening result, if available.

Proportions of Subjects With Virologic Responses and Virologic Failures

For the primary efficacy analysis, the proportions of subjects achieving SVR₁₂ for each GT will be provided and 95% CIs for these rates will be calculated using the Clopper-Pearson method [42]. The same method will be used to analyze all binary endpoints including SVR₄, SVR₈, SVR₂₄, and virologic response rates at TW4, TW8, and end of treatment.

For the primary analyses using the FAS population, the M=F missing data approach will be utilized. In these analyses, only subjects with HCV RNA levels <LLOQ for any type of HCV infection at a given time point will be considered to have achieved the endpoint.

For all analyses conducted using the PP and mFAS populations, the missing data approach of TRD=F will be utilized. In addition, for all analyses based on these 2 populations, a subject will be considered to have achieved a response for a particular endpoint if the HCV RNA levels for the infection he/she had at baseline are <LLOQ. For example, if a subject has HCV RNA levels \geq LLOQ at a particular time point, but those RNA levels correspond to an infection that is of a different GT and/or subtype compared to the infection detected at baseline and the baseline infection has been cleared, then the subject is considered to have achieved response for the given endpoint.

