8.9 Sample Size and Power Calculations

8.9.1 Efficacy Analysis

Approximately 250 subjects will be allocated to treatment with a target allocation of 35 GT1a-, 15 GT1b-, 50 GT2-, 50 GT3-, 50 GT4-, 25 GT5-, and 25 GT6-infected subjects. These sample sizes were chosen to provide sufficient confidence of the estimated treatment response rate for the most prevalent GTs (Section 4.2.3)

Table 18 below shows the 2-sided 95% CIs for SVR_{12} under varying assumptions of the number of successes in the FAS population for each GT. Note that these intervals are not symmetric around the point estimate.

Table 18 Two-Sided 95% Confidence Intervals for SVR12 (FAS Population)

Number of subjects in FAS population	Observed Number of Successes (%)	Two-Sided 95% Confidence Interval ¹
15	15 (100.0%)	(78.2, 100.0)
	14 (93.3%)	(68.1, 99.8)
	13 (86.7%)	(59.5, 98.3)
	12 (80.0%)	(51.9, 95.7)
25	25 (100.0%)	(86.3, 100.0)
	24 (96.0%)	(79.6, 99.9)
	23 (92.0%)	(74.0, 99.0)
	22 (88.0%)	(68.8, 97.5)
35	35 (100.0%)	(90.0, 100.0)
	34 (97.1%)	(85.1, 99.9)
	33 (94.3%)	(80.8, 99.3)
	32 (91.4%)	(76.9, 98.2)
50	50 (100.0%)	(92.9, 100.0)
	49 (98.0%)	(89.4, 99.9)
	48 (96.0%)	(86.3, 99.5)
	47 (94.0%)	(83.5, 98.7)
FAS = Full Analysis Set.		
¹ Based on the Clopper-Pearson method		

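### Section 8.10 estimates subgroup SVR only within each genotype, so cirrhosis and baseline-RAV effects are read in cells too small for any but large differences; add a supplementary genotype-stratified estimate across genotypes

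*Combined protocol and SAP*

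**What the plan says.** Section 8.10 fixes the level of every subgroup analysis: "The subgroup analyses detailed below will be performed within each GT". Its purpose is stated as "To assess the consistency of the response across various subgroups", and the output is SVR12 and SVR24 with 95% CIs in each category of each factor. The factors include baseline RAVs, stage of fibrosis, HIV status and prior treatment.

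The genotype targets in Section 8.9.1 are "35 GT1a-, 15 GT1b-, 50 GT2-, 50 GT3-, 50 GT4-, 25 GT5-, and 25 GT6-infected subjects". Section 2.1 recruits "with a target allocation of approximately 25% to 30% cirrhotic subjects for each GT for GT 1-4", while for the two rarer genotypes "the proportion of cirrhotic subjects allocated for each of these GT5 and GT6 is not stipulated". HIV has no target; Section 4.2.2 says only that "HIV/HCV co-infected subjects will be permitted to enroll in this study". Intervals are exact: "95% CIs for these rates will be calculated using the Clopper-Pearson method" (Section 8.6.1).

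Every efficacy row of Table 15 is also by genotype. Section 8.6.3 defers baseline, PK and exploratory analyses to the sSAP and does not mention subgroups. Secondary objective 3 (Section 3.2) asks for SVR12 in subjects with baseline RAVs, without restricting it by genotype. Section 8.4.1.1 lists no matching endpoint, so the RAV line in 8.10 is the only specified analysis of SVR by RAV status.

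**The concern.** The rationale in Section 4.2.1 is "The development of a single, uniform, and pangenotypic regimen that will be safe and effective in all patient populations". Whether response holds up in cirrhotic, treatment-experienced, HIV co-infected or RAV-carrying subjects is part of that question, and the trial recruits cirrhotic subjects by target so that it can be asked. Splitting them by genotype before estimating anything leaves intervals that overlap under almost any moderate difference.

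Two misreadings follow. Wide overlapping intervals may be taken as evidence of consistency. A deficit common to all genotypes may stand out in one or two tables by chance and be taken for a feature of those genotypes.

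Timing matters too. The sponsor sees results as they accrue (Section 8.2) and monitors efficacy throughout for programme decisions (Section 8.7). An across-genotype analysis added later would be chosen with outcomes in view.

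**Working it through.** **1. The plan's own figures.** Two-sided 95% Clopper-Pearson limits for x responders of n are the beta quantiles B(0.025; x, n−x+1) and B(0.975; x+1, n−x). All 16 rows of Table 18 reproduce to 0.1 point, including 14/15 = (68.1, 99.8) and 15/15 = (78.2, 100).

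**2. Cirrhosis cells.** Per genotype in GT1-4: 50 × 0.25 = 12.5 to 50 × 0.30 = 15. Across GT1-4: 200 × 0.25 = 50 to 200 × 0.30 = 60. GT5-6 may add to this, since no share is set there.

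| Failures | n=12 | n=15 | n=50 | n=60 |
|---|---|---|---|---|
| 0 | 73.5-100 | 78.2-100 | 92.9-100 | 94.0-100 |
| 2 | 51.6-97.9 | 59.5-98.3 | 86.3-99.5 | 88.5-99.6 |

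Expected width, summing binomial probability × interval width over all outcomes at a true SVR of 90%, using 27.5% cirrhotic (50 × 0.275 = 13.75, about 14; 200 × 0.275 = 55): 35.3 points at n=14 and 17.2 points at n=55.

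**3. Baseline-RAV cells.** Section 4.1.2.2.1.2 gives NS5A RAVs at positions 30, 31 and 93 in 7.8% of GT1a, 26.8% of GT1b and 18.5% (23/124) of GT3.
- GT1: 35 × 0.078 + 15 × 0.268 = 2.73 + 4.02 = 6.75, about 7. An outcome of 6/7 gives 42.1-99.6.
- GT3: 50 × 0.185 = 9.25, about 9. An outcome of 8/9 gives 51.8-99.7. (The response counts in the same paragraph, 122 without and 23 with RAVs, imply 23/145 = 15.9%, or about 8.)

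Section 8.10 counts RAVs to either drug class, so actual cells may be larger.

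**4. HIV cells (assumption).** At 5% to 15% co-infected, a 50-subject genotype holds 2.5 to 7.5 such subjects. At 10%, 5/5 gives 47.8-100 within a genotype, and 25/25 over all 250 gives 86.3-100.

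**5. Sizing the loss.** The plan does no testing, so the exact power of a two-sided 5% Fisher comparison is used only as a yardstick. Assumed: non-cirrhotic SVR 97% and the same cirrhotic rate in every genotype.

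| Cirrhotic SVR | One genotype (14 vs 36) | GT1-4 (55 vs 145) |
|---|---|---|
| 80% | 37% | 95% |
| 85% | 21% | 81% |
| 90% | 8% | 48% |

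**6. What four separate tables would show.** With cirrhotic SVR at 80%, the chance that at least one of four tables reaches 5% is 1 − (1 − 0.367)^4 = 84%, and that all four do is 0.367^4 = 2%. At 85% the figures are 1 − (1 − 0.205)^4 = 60% and 0.205^4 = 0.2%. So a shared deficit usually appears somewhere and almost never everywhere.

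**7. When pooling is worse.** Suppose the deficit is in GT3 only: 65% in 14 cirrhotic subjects, 97% in all others. The pooled cirrhotic rate is (14 × 0.65 + 41 × 0.97)/55 = 89%. The same yardstick gives 80% within GT3 and 58% across GT1-4.

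**The case against.** Genotype is the unit of this design: quotas, sample size, efficacy tables and stopping rules are all set by genotype. The documents also expect cirrhosis to act differently by genotype. Section 4.2.1 singles out GT3 cirrhosis as harder to treat, and Table 2 shows one regimen in GT3 at 92-98% in non-cirrhotic and 58-69% in cirrhotic subjects. Step 7 shows that the within-genotype table is the more sensitive one for that pattern. This stands, and it is why the across-genotype display should not outrank the other.

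A reader might infer that the consistency aim is impossible to meet. The documents do not support that. This is an estimation study, the intervals can be produced, and the plan itself tabulates n=15 for GT1b. A very large deficit would show: 60% against 97% gives 87-89% on the yardstick within one genotype. A reader might also infer that a shared deficit would be missed in every genotype table; step 6 shows otherwise. Nor is it established that all other cells are smaller than the cirrhotic ones. HIV numbers are an assumption, and non-cirrhotic cells hold 35 to 38.

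Later pooling would not inevitably be post hoc, because Section 8.0 allows changes to be documented in an sSAP before final database lock. In an open-label trial, though, that change would be made with results visible.

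Finally, a genotype that meets the efficacy criteria may have its regimen extended with RBV added (Section 5.11.4), so crude pooling could mix regimens. That stands and needs a rule.

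The absence of testing does not answer the point. In an estimation study precision is the product, and the proposal is also estimation.

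**Conclusion.** The point holds in a limited form. Within genotype, consistency by cirrhosis and by baseline RAVs, and with the latter secondary objective 3, cannot be assessed with useful precision for any but large differences. Going from about 14 to about 55 cirrhotic subjects roughly halves the expected interval width (35.3 to 17.2 points at 90% SVR). A deficit shared across genotypes would tend to be read as belonging to one or two of them.

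The cell sizes assume that the enrolment targets are met; stopping a genotype early, or displaying by actual treatment, would make cells smaller. The power figures assume 97% in non-cirrhotic subjects and an equal deficit in each genotype. RAV cells rest on three NS5A positions, and HIV cells on an assumed share. Pooling does not rescue small differences: 90% against 97% reaches only 48%. This is a cheap improvement and not a flaw in the primary analysis.

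**What to change.** Keep the within-genotype tables in 8.10 and add, with neither display ranked above the other, a supplementary across-genotype analysis in the FAS with missing counted as failure, for four factors: baseline RAVs, stage of fibrosis, prior treatment and HIV status.

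- Report SVR12 and SVR24 with a Clopper-Pearson 95% CI for each category.
- Report the difference between categories stratified by genotype with Mantel-Haenszel weights, with its 95% CI. Stratification matters most for RAVs, whose prevalence varies strongly by genotype. Strata lacking one category drop out, and strata without failures cause no difficulty.
- State that the result is read beside the within-genotype tables to check for genotype-specific effects, GT3 cirrhosis in particular.
- Show subjects whose regimen was changed to 16 weeks plus RBV separately, in line with Section 8.5.

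The cost is a short addition to 8.10 and one more set of tables from data already collected; enrolment and treatment are untouched. The downside is that pooled rates reflect the genotype quotas and can dilute a deficit confined to one genotype, which is why the within-genotype tables stay.

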8.11 Compliance (Medical Adherence)

In this study, as part of the routine recording of the amount of study treatment taken by each subject, the number of tablets remaining in study packaging will be counted, reviewed, and recorded at regular intervals. These results will be used to calculate subject compliance.

A day within the study will be considered an “On-Therapy” day if the subject takes the assigned treatment MK-3682 (450 mg) + RZR (180 mg) as noted in Section 5.2.

For a subject who is followed for the entire study period, the “Number of Days Should be on Therapy” is the total number of days from allocation to the last scheduled day for treatment administration for that subject. For a subject who discontinued from the study permanently, the “Number of Days Should be on Therapy” is the total number of days from allocation to the date of the last dose of study medication.

For each subject, percent compliance will then be calculated using the following formula:

$$\text{Percent Compliance} = \frac{\text{Number of Days on Therapy}}{\text{Number of Days Should be on Therapy}} \times 100.$$

Summary statistics will be provided on percent compliance for the FAS population.

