5.8 Subject Withdrawal/Discontinuation Criteria

5.8.1 Discontinuation of Treatment

Discontinuation of treatment does not represent withdrawal from the trial.

As certain data on clinical events beyond treatment discontinuation may be important to the study, they must be collected through the subject's last scheduled follow-up, even if the subject has discontinued treatment. Therefore, all subjects who discontinue trial treatment prior to completion of the trial will still continue to participate in the trial as specified in Section 6.0, Trial Flow Chart and Section 7.1.5.6, Discontinued Subjects Continuing to be Monitored in the Trial.

Subjects may discontinue treatment at any time for any reason or be dropped from treatment at the discretion of the investigator should any untoward effect occur. In addition, a subject may be discontinued from treatment by the investigator or the Sponsor if treatment is inappropriate, the trial plan is violated, or for administrative and/or other safety reasons. Specific details regarding procedures to be performed at treatment discontinuation are provided in Section 7.1.4 – Other Procedures.

A subject must be discontinued from treatment but continue to be monitored in the trial for any of the following reasons:

- The subject or subject's legally acceptable representative requests to discontinue treatment.

Table 11 provides reasons why a subject must be discontinued from treatment but should continue to be monitored in the trial, as well as reasons why a subject must be discontinued from treatment and the trial.

Table 11 Discontinuation Scenarios

Reason for Discontinuation Scenario	Action
The subject has a medical condition or personal circumstance which, in the opinion of the investigator and/or Sponsor, places the subject at unnecessary risk through continued participation in the trial or does not allow the subject to adhere to the requirements of the protocol.	Discontinue from Treatment and Trial
Subject meets criteria for HCV virologic breakthrough or rebound (see Section 4.2.3.1.1.2)	Discontinue from Treatment (should continue to monitor in the trial)
Subject becomes pregnant during the trial.	Discontinue from Treatment (should continue to monitor in the trial)
A physician investigator feels it is in the best interest of the subject to discontinue.	Discontinue from Treatment (should continue to monitor in the trial)

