8.1 Statistical Analysis Plan Summary

Key elements of the statistical analysis plan (SAP) are summarized below; the comprehensive plan is provided in Sections 8.2 through 8.12.

Study Design Overview	This is a Phase 2, nonrandomized, multi-site, open-label trial to study the efficacy and safety of the combination regimen of MK-3682 + RZR in subjects with chronic HCV GT1, GT2, GT3, GT4, GT5, or GT6 infection. All subjects will receive MK-3682 450 mg + RZR 180 mg for 12 weeks. Subjects can be treatment-naïve or treatment-experienced with a prior IFN-based therapy, cirrhotic or non-cirrhotic, and mono-infected with HCV or co-infected with HIV. Approximately 250 subjects will be assigned to receive treatment, with target allocation based on GT (GT1, GT2, GT3, GT4, GT5, or GT6). All subjects will be followed for 24 weeks after the end of study therapy.
Treatment Assignment	All subjects will receive MK-3682 + RZR for 12 weeks.
Analysis Populations	Efficacy: Full Analysis Set (FAS), Per Protocol (PP), and modified Full Analysis Set (mFAS). Safety: All Subjects as Treated (ASaT)
Primary Endpoint(s)	Proportion of subjects achieving SVR ₁₂
Key Secondary Endpoints	Proportion of subjects achieving SVR ₂₄ ; Proportion of subjects experiencing virologic failure at FW12 among all subjects who do not discontinue study for non-treatment-related reasons.
Statistical Methods for Key Efficacy Analyses	For the primary efficacy analysis based on the FAS population, the proportions of subjects achieving SVR ₁₂ will be estimated in each GT, and 95% confidence intervals (CIs) for these rates will be calculated using the Clopper-Pearson method [42]. The missing data approach of Missing=Failure (M=F) will be utilized for the primary analysis. The same Clopper-Pearson method will be used to analyze all binary endpoints based on the mFAS population and for the PP population for each GT, and Treatment-Related Discontinuation=Failure (TRD=F) will be used as the missing data approach for both analysis populations.

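### Section 8.11 sets the compliance denominator by study retention rather than by treatment status, so identical exposure can score 33.3% or 100%

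*Combined protocol and SAP*

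**What the plan says.** Section 8.11 defines percent compliance as days on therapy divided by the days the subject should have been on therapy, times 100. The numerator is a count of days: "A day within the study will be considered an “On-Therapy” day if the subject takes the assigned treatment". The denominator has two forms:

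- For those retained throughout, the count of expected treatment days goes "from allocation to the last scheduled day for treatment administration for that subject".
- "For a subject who discontinued from the study permanently", it runs "from allocation to the date of the last dose of study medication".

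The result is summarised for the FAS, which pools both kinds of subject.

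Section 5.8.1 treats stopping treatment and leaving the trial as separate events: "Discontinuation of treatment does not represent withdrawal from the trial". It adds that those who stop treatment early go on participating. All but one of the twelve rows of Table 11 direct that the subject stay under observation after stopping treatment. Section 7.1.5.6 sends early stoppers to an Early Discontinuation visit and then into the follow-up visits. The planned course is 12 weeks (Section 8.1: "All subjects will receive MK-3682 + RZR for 12 weeks"), or 16 weeks for a genotype whose regimen is extended.

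**The concern.** The denominator changes when a subject leaves the study. The event that matters for adherence is the end of treatment. Section 8.11 has no rule keyed to that event, so a subject who stops early and completes follow-up falls under the first denominator and is charged for every day after the stop. A subject with the same dosing history who leaves the study is not.

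The value can even be settled long after the last tablet. Of two subjects who stop at day 28, one who completes Follow-up Week 24 is counted to the last scheduled treatment day. One who drops out at Follow-up Week 16 is counted to the last dose.

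What is at stake is the meaning of a pre-specified summary. For some early stoppers the percentage measures how much of the planned course was completed, and for others how regularly doses were taken before the stop. The pooled figure has no single interpretation.

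**Working it through.** The plan states no compliance figure, so there is nothing to reproduce. The check applies the Section 8.11 formula directly.

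**Inputs from the documents**
- Planned course: 12 × 7 = 84 days; extended course: 16 × 7 = 112 days.
- Denominator if followed to the end of the study: days to the last scheduled treatment day.
- Denominator if the subject left the study: days to the last dose.
- FAS size: about 250.

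**Assumptions, not in the documents**
- The stop day (varied below), with every dose taken up to it.
- The number of early stoppers, and the compliance of everyone else.

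**Per subject, stop at day 28**
- Followed to the end: 28/84 × 100 = 33.3%.
- Left the study: 28/28 × 100 = 100%.

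**Other stop times on the 84-day course**

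| Stop after | Followed | Left the study | Gap (points) |
|---|---|---|---|
| Week 1 | 7/84 = 8.3% | 100% | 91.7 |
| Week 2 | 14/84 = 16.7% | 100% | 83.3 |
| Week 4 | 28/84 = 33.3% | 100% | 66.7 |
| Week 6 | 42/84 = 50.0% | 100% | 50.0 |
| Week 8 | 56/84 = 66.7% | 100% | 33.3 |
| Week 10 | 70/84 = 83.3% | 100% | 16.7 |
| Week 11 | 77/84 = 91.7% | 100% | 8.3 |

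Missed doses do not remove the contrast. With 4 missed in the first 28 days, the scores are 24/84 = 28.6% and 24/28 = 85.7%. Against a 112-day course, a day-28 stop with full adherence scores 28/112 = 25.0% if followed and 100% if not.

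**Effect on the FAS mean** (two day-28 stoppers in 250, the other 248 at 98%)
- Both followed: (248 × 98 + 2 × 33.3)/250 = 97.5%.
- Neither followed: (248 × 98 + 2 × 100)/250 = 98.0%.
- Difference: about half a point.

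**Range for more stoppers** (k day-28 stoppers, all followed, everyone else at 100%): k = 5 gives 98.7%, k = 10 gives 97.3% and k = 20 gives 94.7%. If none of them were followed, the mean would be 100% in each case.

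**With one rule keyed to treatment**, the two day-28 subjects agree: both 100% if counted to the last dose, or both 33.3% if counted to the planned end.

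**The case against.** The strongest textual reply is that the first rule ends at the last scheduled day for that particular subject, and that nothing is scheduled once treatment has been stopped. Both subjects would then score 100%. The text does not say this. The individual wording is naturally explained by 12- versus 16-week courses, and the reading would make the separate last-dose rule largely redundant. If it is what the sponsor meant, a clarifying sentence is still needed.

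The replies on consequence carry more weight, and they stand.

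- Percent compliance enters no endpoint, no listed Per Protocol exclusion (Section 8.5.1) and no stopping rule (Section 5.11).
- A reader might infer that the defect prevents judging whether virologic failures come from poor adherence. The documents do not support that. Section 4.2.5.3 assigns drug compliance at breakthrough to the trough samples, and the diary in Section 7.1.1.8 records doses and is checked against unused drug. Failures can be examined individually whatever the denominator.
- A reader might infer shifts of several points by working in a genotype of 50: two day-28 stoppers with the rest at 98% give (48 × 98 + 2 × 33.3)/50 = 95.4% against (48 × 98 + 2 × 100)/50 = 98.1%. Section 8.11 plans the summary for the FAS and states no summary by genotype.
- A reader might infer that better follow-up lowers compliance generally. It does so only for those who stop treatment early. For someone who finishes treatment and then leaves, the two denominators are essentially the same.
- Early stopping may be rare. In the related three-drug studies, all 240 Part A subjects completed dosing (Section 4.1.2.2.1.1), and 2 of 94 subjects in PN021 had discontinued at the cut-off (Section 4.1.2.2.2). This is indirect evidence, because those regimens use a lower ruzasvir dose plus a third drug.

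**Conclusion.** The point holds as an inconsistency in a stated rule. Section 8.11 scores identical exposure differently according to study retention, and Section 5.8.1 makes the followed early stopper the ordinary case. For an individual the gap is large: about 92 points for a stop at week 1, 66.7 at week 4 and about 8 at week 11, assuming full adherence to the stop on an 84-day course. For the FAS mean it is small: about half a point under the assumption of two day-28 stoppers in 250 with the rest at 98%, taking the extreme contrast of both followed against neither. It grows with the number of early stoppers, which the documents do not predict.

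This is a minor correction to a descriptive summary. It leaves the SVR12 and SVR24 analyses and the stopping rules untouched.

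**What to change.** Replace the two denominators in Section 8.11 with one rule keyed to treatment. The days a subject should be on therapy run from Day 1 to the last dose for any subject who permanently stops treatment early, whether or not still followed. For everyone else they run from Day 1 to the last scheduled dose.

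That measure says nothing about early stopping, because a fully adherent subject who stops at day 28 scores 100%. It is therefore best read beside a completion figure: days on therapy divided by planned days (84, or 112 if extended) for all FAS subjects. This second figure is optional, since Section 8.12 already summarises days on therapy.

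The cost is one changed sentence and at most one extra summary column. No new data are needed, because diary entries, pill counts and last-dose dates are already collected. Section 8.0 lets such a change be recorded in the supplemental SAP before final database lock.
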